6.2. Preparation, handling, storage, and accountability

The study interventions must be stored in a secured place within the temperature range specified on the study intervention's label. The storage temperature should be continuously monitored and recorded with a calibrated (if not validated) temperature monitoring device(s).

Only authorized study personnel should be allowed access to the study interventions. Storage conditions will be assessed by a sponsor study contact during pre-study activities. Refer to the Pharmacy Manual for more details on storage and handling of the study interventions.

6.3. Measures to minimize bias: randomization and blinding

6.3.1. Participant identification

Participant identification numbers will be assigned sequentially to the participants who have consented to participate in the study, according to the range of participant identification numbers allocated to each study center.

6.3.2. Randomization to study intervention

Approximately 400 eligible participants will be randomly assigned (1:1) to the 2 study groups (Co-administration and Staggered).

The numbering of *Rotarix* PCV-free and IPV supplies will be performed at GSK, using a block scheme randomization in MATerial EXcellence, a program developed by GSK. Entire blocks will be shipped to the study centers/warehouse(s).

To allow GSK to take advantage of greater rates of recruitment than anticipated in this study and to thus reduce the overall study recruitment period, an over-randomization of supplies will be prepared.

6.3.3. Intervention allocation to the participant

The system's randomization algorithm will use a minimization procedure accounting for center and the study as a whole as minimization factors. Minimization factors will have equal weight in the minimization algorithm.

Once a participant identification number is allocated, the randomization system will determine study group and will provide the study intervention number to be used for the first dose. The study intervention number(s) to be used for subsequent dosing will be provided by the same automated Internet-based system (Source Data Base for Internet Randomization [SBIR]).

When SBIR is not available, please refer to the SBIR user guide or Pharmacy Manual for specific instructions.

Refer to the Pharmacy Manual for additional information about the study intervention number allocation.

6.3.4. Blinding and unblinding

The study will be conducted in an open-label manner with respect to *Rotarix* PCV-free and IPV.

6.4. Study intervention compliance

Study intervention administration will be performed under medical supervision. The date of each dose administered in the study center will be recorded in the source documents and in the eCRF.

6.5. Dose modification

This section is not applicable.

6.6. Continued access to study intervention after the end of the study

This section is not applicable.

6.7. Treatment of overdose

This section is not applicable.

6.8. Concomitant therapy

At each study visit, the investigator or their delegate should question the participant's parent(s)/LAR(s) about all medications/products taken, and vaccinations received by the participant.

The following concomitant medication(s)/product(s)/vaccine(s) must be recorded in the eCRF:

- All concomitant medications/products, except vitamins and dietary supplements, administered following each dose of study interventions (Day 1 to Day 31).
- All concomitant vaccinations from Visit 1 up to the Visit 7 (blood sample visit).
- All concomitant medication leading to discontinuation of the study intervention or elimination from the analysis, including products/vaccines (Please refer to the sections [5.2.2](#) and [9.2.1](#) for further details).

- Prophylactic medication (i.e., medication administered in the absence of ANY symptom and in anticipation of a reaction to the study intervention administration) e.g., an anti-pyretic is considered to be prophylactic when it is given in the absence of fever and any other symptom, to prevent fever from occurring [fever is defined as temperature $\geq 37.5^{\circ}\text{C}$. The preferred location for measuring temperature in this study will be the axilla].
- All concomitant medication which may explain/cause/be used to treat an SAE including vaccines/products, as defined in Sections 8.3.1 and 10.3.6.1. These must also be recorded in the Expedited AE report.

The Local Medical Lead (LML) should be contacted if there are any questions regarding concomitant or prior therapy.

7. DISCONTINUATION OF STUDY INTERVENTIONS AND PARTICIPANT DISCONTINUATION/WITHDRAWAL

7.1. Discontinuation of study interventions

‘Discontinuation’ of study interventions refers to any participant who has not received all planned doses of the study interventions. A participant who discontinued the study interventions may continue other study procedures (e.g., safety or immunogenicity), planned in the study protocol at the discretion of the investigator.

The primary reason for premature discontinuation of the study interventions will be documented on the eCRF as follows:

- AE requiring expedited reporting to GSK
- Unsolicited nonserious AE
- Solicited AE
- Protocol deviation
- Not willing to be vaccinated
- Migrated/moved from study area
- Other (specify).

7.1.1. Contraindications to subsequent study interventions administration

The eligibility for subsequent study interventions administration must be confirmed before administering any additional dose.

Participants who meet any of the criteria listed below or criteria listed in Section 5.2.1, Section 5.2.2, Section 5.2.3 and Section 5.2.4 should not receive additional doses of study intervention. Such participants should be encouraged to continue other study procedures, at the investigator's discretion (Section 10.3.6.3). All relevant criteria for discontinuation of study intervention administration must be recorded in the eCRF.

- Participants who experience any SAE judged to be possibly or probably related to study intervention or non-study concomitant vaccine/product, including hypersensitivity reactions.
- Participants who develop any new condition which, in the opinion of the investigator, may pose additional risk to the participants if they continue to participate in the study.
- Anaphylaxis following the administration of study interventions.
- Any condition that in the judgment of the investigator would make intramuscular injection unsafe.

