5.2.1. Medical conditions

- History of any reaction or hypersensitivity likely to be exacerbated by any component of the study interventions.
- Any confirmed or suspected immunosuppressive or immunodeficient condition, based on medical history and physical examination (no laboratory testing required).
- Hypersensitivity to latex.
- History of severe combined immunodeficiency.
- History of seizures or progressive neurological disease.
- Family history of congenital or hereditary immunodeficiency.
- Uncorrected congenital malformation (such as Meckel's diverticulum) of the gastrointestinal tract that would predispose for intussusception (IS).
- History of IS.
- Major congenital defects, or serious chronic illness as assessed by the investigator.
- Any contraindications to IPV.
- Previous confirmed occurrence of rotavirus gastroenteritis (RVGE).
- History of poliomyelitis.
- Participants with confirmed or suspected Coronavirus Disease 2019 (COVID-19).

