5.2.2. Prior/Concomitant therapy

- Use of any investigational or non-registered product (drug, vaccine or invasive medical device) other than the study interventions during the period beginning 30 days before the first dose of study interventions (Day -29 to Day 1), or planned use during the study period.
- Planned administration/administration of a vaccine not foreseen by the study protocol in the period starting 30 days before the first dose and ending 30 days after the last dose of study interventions administration*, with the exception of the inactivated influenza vaccine, which is allowed at any time during the study and other licensed routine childhood vaccinations.
 - *In case emergency mass vaccination for an unforeseen public health threat (e.g., a pandemic) is recommended and/or organized by public health authorities outside the routine immunization program, the time period described above can be reduced if, necessary for that vaccine, provided it is used according to the local governmental recommendations and that the Sponsor is notified accordingly.
- Administration of long-acting immune-modifying drugs from birth or planned administration at any time during the study period (e.g., infliximab).
- Administration of immunoglobulins and/or any blood products or plasma derivatives from birth or planned administration during the study period.
- Chronic administration (defined as more than 14 days in total) of immunosuppressants or other immune-modifying drugs since birth. For corticosteroids, this will mean prednisone ≥ 0.5 milligram/kilogram (kg)/day, or equivalent. Inhaled, intra-articular and topical steroids are allowed.
- Previous vaccination against RV.
- Previous vaccination against poliomyelitis.

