5.5. Criteria for temporarily delaying enrolment and/or study intervention administration

Enrolment/study intervention administration may be postponed within the permitted time interval until transient conditions cited below are resolved:

- Non-rotavirus GE within 7 days preceding the study intervention administration.
- Acute disease and/or fever at the time of enrolment and/or study intervention administration. Refer to the SoA (Section 1.3) for fever definition and preferred location for measuring temperature in this study.
- Participants with a minor illness (such as mild diarrhea, mild upper respiratory infection) without fever may be enrolled and/or vaccinated at the discretion of the investigator.
- Participants with known COVID-19 positive contacts within the past 14 days.

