Original legible documents, data, and records (e.g., hospital records, clinical and office charts, laboratory notes, memoranda, participants' diaries or evaluation checklists, pharmacy dispensing records, recorded data from automated instruments, copies or transcriptions certified after verification as being accurate copies, microfiches, photographic negatives, microfilm or magnetic media, x-rays, participant files, and records kept at the pharmacy, laboratories and at medico-technical departments involved in the clinical study).

Study intervention:

Any investigational or marketed product(s) or placebo intended to be administered to a participant during the study.

Study monitor:

An individual assigned by the sponsor and responsible for assuring proper conduct of clinical studies at 1 or more investigational sites.

Unsolicited adverse event:

Any AE reported in addition to those solicited during the clinical study. Also, any 'solicited' symptom with onset outside the specified period of follow-up for solicited symptoms will be reported as an unsolicited adverse event.

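### Section 7.1.1 stops study IPV as well as Rotarix after confirmed rotavirus gastroenteritis that is not a related SAE, and no IPV-related reason is given

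*Protocol*

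**What the plan says.** Protocol Section 7.1.1 requires eligibility to be reconfirmed before each further dose. Infants who meet its own bullets, or a criterion in "Section 5.2.1, Section 5.2.2, Section 5.2.3 and Section 5.2.4 should not receive additional doses of study intervention", are stopped. They may continue other study procedures.

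The glossary (10.8.2) defines study intervention as "Any investigational or marketed product(s) or placebo intended to be administered to a participant during the study", and Section 4.1 names both IPV and Rotarix PCV-free as study interventions.

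Among the criteria carried forward from 5.2.1 is "Previous confirmed occurrence of rotavirus gastroenteritis (RVGE". IPV has its own separate item, "Any contraindications to IPV". Section 5.5 allows postponement for gastroenteritis only when it is not rotavirus: "Non-rotavirus GE within 7 days preceding the study intervention administration".

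One of the bullets in 7.1.1 is "Any condition that in the judgment of the investigator would make intramuscular injection unsafe". It too leads to a stop of study intervention, although Rotarix is given by mouth (Table 7).

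In SAP Section 6.1.3, code 2070 eliminates from the PPS infants with RVGE up to the Visit 7 blood sample. Code 1070 eliminates infants who did not receive all doses of both vaccines.

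**The concern.** A bar on further Rotarix after confirmed RVGE is a rotavirus matter. By referring to study intervention as a whole, the rule also withholds polio vaccine. Once the second Rotarix dose has been given, the RVGE criterion has no Rotarix dose left to stop, so all it can do is withhold IPV. Neither document explains why IPV should stop, and the listing of IPV contraindications as a separate item suggests that RVGE was not regarded as one.

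What is at stake is the timely polio vaccination of the few infants affected. In the other direction, it is the second oral Rotarix dose for an infant who cannot safely have an intramuscular injection.

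**Working it through.** No figure in the plan states the size of this effect. The check therefore works from the text and from the visit schedule.

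**1. Which infants are caught by this criterion alone?**
- RVGE that is serious and judged related is already stopped by the related-SAE bullet of 7.1.1.
- RVGE that in the investigator's opinion poses additional risk is already stopped by the new-condition bullet.
- What remains is confirmed RVGE that is non-serious, or serious but unrelated. For these infants only the carried-forward 5.2.1 item stops IPV, and no text limits that item to Rotarix.

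**2. When can the rule withhold only IPV?** The inputs are the intervals in protocol Tables 3 and 4, in days from Visit 1.
- Staggered, optimal: Rotarix on days 0 and 30; IPV on days 15, 45 and 75. IPV-only period = 75 − 30 = 45 of 75 dosing days (60%).
- Staggered, allowed: Visit 3 on days 28–36; Visit 6 on days 14 + 28 + 28 = 70 to 18 + 36 + 36 = 90. Period 70 − 36 = 34 days (34/70 = 49%) to 90 − 28 = 62 days (62/90 = 69%).
- Co-administration, optimal: Rotarix on days 15 and 45; IPV on days 15, 45 and 75. IPV-only period = 75 − 45 = 30 of 60 dosing days (50%).
- Co-administration, allowed: 28–36 days, which is 28/(36 + 28) = 44% to 36/(28 + 36) = 56%.

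**3. Doses withheld, by day of event (optimal intervals)**

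| Group | Event day | IPV doses withheld | Rotarix doses withheld |
|---|---|---|---|
| Staggered | 0–15 | 3 | 1 |
| Staggered | 15–30 | 2 | 1 |
| Staggered | 30–45 | 2 | 0 |
| Staggered | 45–75 | 1 | 0 |
| Co-administration | 15–45 | 2 | 1 |
| Co-administration | 45–75 | 1 | 0 |

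The national programme uses IPV for doses 1 and 2 and OPV for dose 3 (Section 2.1). Within the IPV-only period, the only programme IPV dose at risk is therefore dose 2 in the Staggered group. It is at risk for 45 − 30 = 15 days (allowed range 42 − 36 = 6 to 54 − 28 = 26).

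**4. How many infants?** The documents give no incidence of RVGE. The study collects blood only, so RVGE would have to be confirmed outside it. As an assumption, let r be the risk of a triggering event over the dosing period, evenly spread, with r from 0.1% to 1%.
- Any time in the dosing period: 400r = 0.4 to 4 infants.
- In the IPV-only period: 200r × (0.60 + 0.50) = 220r = 0.22 to 2.2 infants.

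The sample size already allows for 400 × 20% = 80 infants who are not evaluable.

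**5. Does it touch the analysis?**
- Primary PPS: an infant with RVGE leaves under code 2070 whether or not IPV continues. An infant who cannot have IPV leaves under code 1070 whether or not Rotarix continues.
- Exposed Set repeat: this is run only if exclusions from the PPS reach the 5% threshold (SAP Sections 3 and 4.2.3). An under-dosed infant who still gives a Visit 7 sample could count there as a non-responder. For scale, the Miettinen–Nurminen lower limit is −4.93% for 188/200 against 188/200. With two fewer responders in Staggered (188/200 v 186/200) it is −4.04%. With two fewer in Co-administration (186/200 v 188/200) it is −6.13%. All three clear −10%.

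**The case against.** The best defence is that stopping both vaccines is a cautious and simple rule. The trial tests a two-vaccine schedule, and the SAP treats RVGE as an infection that may influence the immune response. Once such an infant has left the PPS, ending study dosing is coherent. This is fair as far as it goes, but it is a reason about analysis and not a clinical reason to withhold IPV. Because the infant leaves the PPS in either case, stopping IPV protects nothing in the primary analysis. The part that stands is that very few infants are involved.

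A reader might infer more than the documents support:

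- **That IPV should also continue after intussusception or another SAE attributed to Rotarix.** Section 7.1.1 stops study intervention after any related SAE, and 10.3.7.2 attributes an event to all interventions when the cause cannot be assigned. Nothing in the documents shows that rule to be wrong. What is left is intussusception judged unrelated, or a gut malformation found only after enrolment; both are too remote to carry the point.
- **That affected infants are barred from polio vaccine.** Section 5.2.2 qualifies its vaccine restriction with an exception for influenza vaccine, "which is allowed at any time during the study and other licensed routine childhood vaccinations". Catch-up outside the study is therefore not forbidden by that section. SAP code 1040 does list non-study IPV among forbidden vaccines, but it is a rule for eliminating infants from the PPS, and these infants have already left it.
- **That sites will handle the rule differently.** The text is clear, and Section 8 permits waivers only for immediate safety concerns. A site that continued IPV would be deviating.
- **That the carried-forward previous-vaccination items bar dose 2.** The protocol itself schedules dose 2 (Section 4.2), so this is only drafting. So is the COVID-19 item, "Participants with confirmed or suspected Coronavirus Disease 2019 (COVID-19"; Section 5.5 already allows delay for acute disease, fever and recent contact.

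**Conclusion.** The point holds as a minor one about infant protection. As written, confirmed RVGE after dose 1 that is not a related SAE stops study IPV, including after Rotarix dosing is complete, and no IPV-related reason is given. The mirror case, unsafe intramuscular injection stopping oral Rotarix, follows from the same wording.

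The reading of the text and the timing in steps 1 to 3 rest on the documents. The counts (0.4 to 4 infants overall, 0.22 to 2.2 in the IPV-only period) rest on the assumed risk of 0.1% to 1% and on even spread over time, neither of which the documents supply.

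A reader might infer that the non-inferiority conclusion is at risk. The documents do not support that. The primary PPS result is unchanged, and a visible effect on the conditional Exposed Set repeat is a remote possibility. This is a change to consider, not one that the trial depends on.

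**What to change.** Amend Section 7.1.1 in two places:

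- Confirmed RVGE that is not a related SAE stops further Rotarix only. IPV continues on schedule once the infant is well, unless an IPV contraindication or another bullet of 7.1.1 applies.
- A condition whose only effect is to make intramuscular injection unsafe stops IPV but not oral Rotarix.

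Leave the related-SAE, anaphylaxis and new-condition bullets as they are, so that any related SAE, including related intussusception, still stops both vaccines.

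The cost is a short protocol amendment, which needs IRB/IEC approval before it is implemented (Section 10.1.1), and a note to sites. No visits, samples or SAP analyses are added, and codes 2070 and 1070 can stay as written. The return is timely polio vaccination for a handful of infants at most.

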7.2. Participant discontinuation/withdrawal from the study

A participant is considered to have withdrawn from the study if no new study procedure has been performed or no new information has been collected for them since the date of withdrawal/last contact.

From an analysis perspective, a study 'withdrawal' refers to any participant who did not return for the concluding visit planned in the protocol.

Investigators will attempt to contact participants who do not return for scheduled visits or follow-up.

All data and samples collected up to and including the date of withdrawal of/last contact with the participant will be included in the study analyses.

The primary reason for study withdrawal will be documented in the eCRF, based on the list below:

- Adverse events requiring expedited reporting to GSK (please refer to the section 10.3.8.1 for the details)
- Unsolicited nonserious AE
- Solicited AE
- Protocol deviation
- Withdrawal by participant, not due to an AE*
- Migrated/Moved from the study area
- Lost to follow-up

- Sponsor study termination
- Other (specify)

*If a participant is withdrawn from the study because the participant's parent(s)/LAR(s) has withdrawn consent and the reason for withdrawal was provided, the investigator must document this reason in the eCRF.

Participants who are withdrawn from the study because of AEs/SAEs must be clearly distinguished from participants who are withdrawn for other reasons. Investigator will follow participants who are withdrawn from the study due to an AE/SAE until the event is resolved (see Section [10.3.6.3](#)).

7.3. Lost to follow-up

Participants will be considered 'lost to follow-up' if their parent(s)/LAR(s) fail to return for scheduled visits and cannot be contacted by the study site.

Please refer to the Pharmacy Manual for a description of actions to be taken before considering the participant lost to follow-up.

8. STUDY ASSESSMENTS AND PROCEDURES

Protocol waivers or exemptions are only permitted when necessary for the management of immediate safety concerns for the participant.

Immediate safety concerns should be discussed with the sponsor as soon as they occur or when the study team becomes aware of them. The purpose of this communication is to determine if the participant(s) should discontinue the study intervention.

Study procedures and their timing are summarized in the SoA (Section [1.3](#)). Adherence to the study design requirements, including those specified in the SoA, is essential and required for study conduct.

All screening evaluations must be completed, and the results reviewed before confirming that potential participants meet all eligibility criteria.

The investigator will maintain a log of all participants screened. All relevant information, such as confirmation of eligibility and reasons for screening failure will be mentioned in this screening log.

Procedures conducted as part of routine clinical management (e.g., hematologic profiles), and obtained before the participant's parent(s)/LAR(s) signed the Informed Consent Form (ICF), may be used for screening and/or for establishing a clinical baseline (provided the procedure met protocol specified criteria and was performed within the time frame defined in the SoA [Section [1.3](#)]).

The Pharmacy Manual provides the investigator and site personnel with detailed administrative and technical information that does not impact participant safety.

During special circumstances (e.g., COVID-19 pandemic), the specific guidance from local public health and other competent authorities regarding the protection of individuals' welfare must be applied. For the duration of such special circumstances, the following measures may be implemented for enrolled participants:

- Biological samples may be collected at a different location* other than the study site or at participant's home. Biological samples should not be collected if they cannot be processed in a timely manner or appropriately stored until the intended use.
- If despite best efforts it is not possible to collect the biological samples within the interval predefined in the protocol, then the interval may be extended up to a maximum length of 60 days (see [Table 3](#) and [Table 4](#)).
- If despite best efforts it is not possible to administer Dose 2 of *Rotarix* PCV-free according to the intervals defined in [Table 3](#) and [Table 4](#), a maximum age of 24 weeks as per the label used outside of China may be used.

*It is the investigator's responsibility to identify an alternate location. The investigator should ensure that this alternate location meets International Council on Harmonization (ICH) Good Clinical Practice (GCP) requirements, such as adequate facilities to perform study procedures, appropriate training of the staff and documented delegation of responsibilities in this location. This alternate location should be covered by proper insurance for the conduct of study on participants by investigator and staff at a site other than the designated study site. Refer to EMA Guidance on the Management of Clinical Trials during the COVID-19 (Coronavirus) pandemic (version 5, 10 February 2022) for more details.

